NCT03349996 Unique Protocol ID: ID3-20170704**PROTOCOL SYNOPSIS: BELSTREAM study**

| | | |
|---------------------------|--|---|
| Title | Belgian Physician-Initiated Trial Investigating the Lifestream Peripheral Stent Graft System for the treatment of complex TASC C and D iliac lesions | |
| Objective | The objective of this clinical investigation is to evaluate, in a controlled setting, the long-term (up to 60 months) safety and efficacy of the Lifestream Peripheral Stent Graft System (Bard) in clinical settings post CE-certification when used according to the indications of the IFU. | |
| Methodology | Prospective, multi-center, physician-sponsored clinical study | |
| Enrollment | 70 subjects | |
| Primary Endpoint | Efficacy endpoint | The primary endpoint of the study is primary patency at 12 months , defined as a target lesion without a hemodynamically significant stenosis on duplex ultrasound (>50%, systolic velocity ratio greater than 2.5) and with freedom from Target Lesion Revascularization (TLR) within 12 months. TLR is defined as a repeated intervention to maintain or re-establish patency within the region of the treated arterial vessel plus 5mm proximal and distal to the treated lesion edge. |
| | Safety endpoint | The primary safety endpoint of the study is the freedom of periprocedural Serious Adverse Events (SAEs), defined according to ISO 14155:2011 as any clinical event that is fatal, life-threatening, or judged to be severe by the investigator; resulted in persistent or significant disability; necessitated surgical or percutaneous intervention; or required prolonged hospitalization. |
| Secondary Endpoint | 1. | Primary patency rate at 1-, 6-, 24-, 36-, 48- and 60 month follow-up. Patients that present without a hemodynamically significant stenosis at the target area on duplex ultrasound (>50%, systolic velocity ratio greater than 2.5) and without prior TLR are defined as being primary patent at the given follow-up. |
| | 2. | Stent graft occlusion rate at pre-discharge, 1-, 6-, 12-, 24-, 36-, 48-, and 60-month follow-up. |
| | 3. | Ankle Brachial Index (ABI) at 1-, 6-, 12-, 24-, 36-, 48- and 60 month follow-up compared with the baseline ABI. |
| | 4. | Amputation rate at 1-, 6-, 12-, 24-, 36-, 48- and 60 month follow-up, defined as any amputation above the knee. |
| | 5. | Technical success, defined as the ability to achieve final residual angiographic stenosis no greater than 30%. |
| | 6. | Clinical success at follow-up is defined as an improvement of Rutherford classification at 1-, 6-, 12-, 24-, 36-, 48- and 60 -month follow-up of one class or more as compared to the pre-procedure Rutherford classification. |
| Inclusion Criteria | General inclusion criteria | |
| | 1. | Corresponding to the CE-mark indications/contra-indications and according to the current medical guidelines for minimally invasive peripheral interventions. |
| | 2. | Patient presenting with a stenotic or occlusive lesion at the iliac arteries suitable for stenting (on indication for primary stenting, based on the discretion of the investigator) |
| | 3. | Patient presenting a score from 2 to 4 following Rutherford classification |
| | 4. | Patient is willing to comply with specified follow-up evaluations at the specified times for the duration of the study |
| | 5. | Patient is >18 years old |

| | |
|--|--|
| | 
6. Patient (or their legal representative) understands the nature of the procedure and provides written informed consent, prior to enrolment in the study
 
7. Patient is eligible for treatment with the Lifestream Peripheral Stent Graft System (Bard)
 |
| Angiographic inclusion criteria | |
| | 
1. The target lesion is either a modified TASC-II class C or D lesion with one of the listed specifications:
 
 ○ Type C lesions 
 ● Bilateral Common Iliac Artery occlusions ● Bilateral External Iliac Artery stenoses 3–10 cm long not extending into the Common Femoral Artery ○ Type D lesions 
 ● Unilateral occlusions of both Common Iliac and External Iliac Artery ● Diffuse disease involving the aorta bifurcation ● Bilateral occlusions of External Iliac Artery |
| | 
2. The target lesion has angiographic evidence of stenosis or restenosis post PTA >50% or occlusion which can be passed with standard guidewire manipulation
 |
| | 
3. There is angiographic evidence of a patent Common and Deep Femoral Artery
 |
| Exclusion criteria | 
1. PTA is technically not possible (not feasible to access the lesion or a defect with the guidewire or balloon catheter)
 
2. Presence of an aneurysm immediately adjacent to the site of stent graft implantation
 
3. Lesions in or adjacent to essential collaterals(s)
 
4. Lesions in locations subject to external compression
 
5. Heavily calcified lesions resistant to PTA
 
6. Patients with diffuse distal disease resulting in poor stent graft outflow
 
7. Patients with a history of coagulation disorders
 
8. Patients with aspirin allergy or bleeding complications and patients unable or unwilling to tolerate anticoagulant/antiplatelet therapy and/or non-responders to anticoagulant/antiplatelet therapy
 
9. Fresh thrombus formation
 
10. Patients with known hypersensitivity to the stent material (L605) and/or PTFE
 
11. The target lesion is either a modified TASC-II class C or D lesion with aortic or common femoral lesion involvement: 
 ○ Type C lesions 
 ● Unilateral External Iliac Artery stenosis extending into the Common Femoral Artery ● Unilateral External Iliac Artery occlusion that involves the origins of the Internal Iliac and/or Common Femoral Artery ● Heavily calcified unilateral External Iliac Artery occlusion with the involvement of the Common Femoral Artery ○ Type D lesions 
 ● Infra-renal aortoiliac occlusion ● Iliac stenoses in patients with an Abdominal Aortic Aneurysm (AAA) requiring treatment and not amenable to endograft placement or 
 |

| | |
|---------------------|---|
| | 
other lesions requiring open aortic or iliac surgery
 
 Diffuse multiple stenoses involving the unilateral Common Iliac, External Iliac and Common Femoral Artery |
| 12. | Previously implanted stent(s) at the same lesion site |
| 13. | Reference segment diameter is not suitable for the available stent graft design |
| 14. | Untreatable lesion located at the distal outflow arteries |
| 15. | Use of alternative therapy (e.g. atherectomy, cutting balloon, DCB, laser, radiation therapy) as part of the index procedure |
| 16. | Patients refusing treatment |
| 17. | Patients for whom antiplatelet therapy, anticoagulants or thrombolytic drugs are contraindicated |
| 18. | Patients who exhibit persistent acute intraluminal thrombus of the proposed lesion site |
| 19. | Perforation at the angioplasty site evidenced by extravasation of contrast medium |
| 20. | Patients with a history of prior life-threatening contrast medium reaction |
| 21. | Patients with uncorrected bleeding disorders |
| 22. | Female patient with child bearing potential not taking adequate contraceptives or currently breastfeeding |
| 23. | Life expectancy of less than twelve months |
| 24. | Any planned surgical intervention/procedure within 30 days of the study procedure |
| 25. | Any patient considered to be hemodynamically unstable at onset of procedure |
| P.I. | [name], ZNA Campus Stuivenberg, Antwerp, Belgium |
| Study conduct | The study will be conducted in accordance with the Declaration of Helsinki and ISO 14155:2011, and comply with requirements regarding Ethics Committees and any other applicable regulations |
| Participating sites | 
 A.Z. Groeninge, Kortrijk, Belgium: [name]Z. Sint-Blasius, Dendermonde, Belgium: [name] Hospital, Bonheiden, Belgium: [name]L.V. Hospital, Aalst, Belgium: [name]Z. H.H., Tienen, Belgium: [name]O.L., Genk, Belgium: [name]N.A. Stuivenberg, Antwerpen, Belgium: [name] |

Table 1. Study Investigations

| Time | | Tests and Procedures |
|---|----------------------|--|
| Pre-Procedure (up to 24 hours before procedure, unless otherwise noted.) | 1. 2. 3. 4. | Medical History Medication Registration Physical Exam Rutherford Categorization and ABI |
| Procedure | 1. 2. 3. 4. | Angiography, pre-procedure Study inclusion Intervention Rutherford Categorization and ABI |
| One day Post-Procedure | 1. 2. 3. | Medication Registration Physical Examination Rutherford Categorization and ABI |
| One month Follow-up (\pm 7 days) | 1. 2. 3. 4. | Medication Registration Physical Examination Rutherford Categorization and ABI Colour Flow Doppler Ultrasound |
| Six month Follow-up (\pm 30 days) | 1. 2. 3. 4. | Medication Registration Physical Examination Rutherford Categorization and ABI Colour Flow Doppler Ultrasound |
| One year Follow-up (\pm 30 days) | 1. 2. 3. 4. | Medication Registration Physical Examination Rutherford Categorization and ABI Colour Flow Doppler Ultrasound |
| Two year Follow-up (730 ± 30 days) | 1. 2. 3. 4. | Medication Registration Physical Examination Rutherford Categorization and ABI Colour Flow Doppler Ultrasound |
| Three year Follow-up (1095 ± 30 days) | 1. 2. 3. 4. | Medication Registration Physical Examination Rutherford Categorization and ABI Colour Flow Doppler Ultrasound |
| Four year Follow-up (1460 ± 30 days) | 1. 2. 3. 4. | Medication Registration Physical Examination Rutherford Categorization and ABI Colour Flow Doppler Ultrasound |
| Five year Follow-up (1825 ± 30 days) | 1. 2. 3. 4. | Medication Registration Physical Examination Rutherford Categorization and ABI Colour Flow Doppler Ultrasound |

- Statistical Analysis Plan (SAP)

Descriptive data summaries will be used to present and summarize the collected data. For categorical variables (e.g. Gender) frequency distributions and cross tabulations will be given. For numeric variables (e.g. Patient age) minimum, maximum, mean, median and standard deviation will be calculated. For all variables a 95% confidence interval for the relevant parameters of the underlying distribution will be calculated. For all time-dependent events life-tables will be calculated using the Kaplan Meier estimate method, for a period starting on the date of the procedure up to and including the 60-month follow-up visit. Stratification to pre-procedural risk factors, Rutherford and lesion criteria will be performed and the log rank test will be used to compare between the different outcomes, associated p-values < 0.05 are defined as significant.

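### Does the unstated unit of analysis for patency and occlusion, with bilateral lesions eligible, undermine the planned analyses?

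*Combined protocol and SAP*

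**What the plan says.** Three endpoints in the Protocol Synopsis use three different nouns:

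- **Primary Endpoint, efficacy (12 months):** patency is "defined as a target lesion without a hemodynamically significant stenosis on duplex ultrasound", together with freedom from target lesion revascularization (TLR).
- **Secondary Endpoint 1 (1, 6, 24, 36, 48 and 60 months):** "Patients that present without a hemodynamically significant stenosis at the target area on duplex ultrasound", and with no earlier TLR, count as patent at that visit.
- **Secondary Endpoint 2:** "Stent graft occlusion rate at pre-discharge" and at each later visit, with no denominator given.

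Angiographic inclusion criterion 1 says which lesions qualify: "The target lesion is either a modified TASC-II class C or D lesion with one of the listed specifications". Three of its five patterns are bilateral: "Bilateral Common Iliac Artery occlusions", "Bilateral External Iliac Artery stenoses" (within a length range) and "Bilateral occlusions of External Iliac Artery". A fourth is "Unilateral occlusions of both Common Iliac and External Iliac Artery". The fifth is diffuse disease at the aortic bifurcation, with no side stated.

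The SAP section is one paragraph. It plans descriptive summaries, 95% confidence intervals for all variables, Kaplan-Meier life-tables from the procedure date to 60 months, and log-rank tests at p < 0.05 across risk-factor, Rutherford and lesion strata. It names no unit of analysis and does not mention correlation within a patient. Enrolment is 70 subjects, with no sample size derivation.

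**The concern.** A patient treated on both sides could contribute one observation, two sides, or several grafts. The two sides share the same patient, risk factors and procedure, so their outcomes are probably positively correlated. Ordinary binomial intervals, Kaplan-Meier standard errors and log-rank tests all assume independent units. If sides or grafts were counted with these methods, the intervals would be too narrow. P-values for factors shared by both sides, such as pre-procedural risk factors, would be too small.

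The estimate itself would also move. A patient who must be patent on both sides is patent less often than a single side, so two analysts choosing different units would report different headline rates from the same data. With bilateral disease written into eligibility, this is a fair question to raise.

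**Working it through.** **Step 1: what the wording supports.** Criterion 1 calls the whole qualifying pattern the target lesion, in the singular, and bilateral patterns are among those listed. A patient with bilateral common iliac occlusions therefore has one target lesion that covers both sides. Two consequences follow:

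- The 12-month definition (a target lesion free of significant stenosis) and Secondary Endpoint 1 (patients free of significant stenosis at the target area) describe the same unit.
- A significant stenosis on either side means the target lesion is not free of stenosis. The rule for combining sides is thus implied, though not spelled out.

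The singular treated vessel in the TLR definition does not point to a per-side unit, because the unilateral pattern itself spans two named arteries. With one result per patient, the observations are independent and the planned methods apply as they stand.

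**Step 2: size if sides were counted instead.** The plan has no figure of its own to reproduce. From the documents: n = 70. Assumed, because the documents give none of these: bilateral share b = 0.6, per-side 12-month patency p = 0.9, within-patient correlation ρ = 0.5 (range 0.2 to 0.8). Three of five patterns is not a share of patients; b is only an illustration.

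- Sides: N = n(1 + b) = 70 × 1.6 = 112.
- Design effect: (N + 2ρnb)/N = (112 + 2 × 0.5 × 42)/112 = 1.375.
- Naive half-width: 1.96 × √(0.9 × 0.1/112) = 5.6 points.
- Clustered half-width: 5.56 × √1.375 = 6.5 points.
- Both sides patent: p² + ρp(1 − p) = 0.81 + 0.045 = 0.855.
- Patient-level patency: 0.6 × 0.855 + 0.4 × 0.9 = 87.3%.
- Patient-level half-width: 1.96 × √(0.873 × 0.127/70) = 7.8 points.

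| | ρ = 0.2 | ρ = 0.5 | ρ = 0.8 |
|---|---|---|---|
| Design effect | 1.15 | 1.375 | 1.60 |
| Per side, naive half-width (points) | 5.6 | 5.6 | 5.6 |
| Per side, clustered half-width (points) | 6.0 | 6.5 | 7.0 |
| Per-patient patency (%) | 85.7 | 87.3 | 88.9 |
| Per-patient half-width (points) | 8.2 | 7.8 | 7.4 |
| Naive Wilson coverage, sides (%) | 94.4 | 92.5 | 89.8 |
| Log-rank, sides, to 12 months (%) | 6.9 | 9.4 | 12.6 |
| Log-rank, sides, to 60 months (%) | 7.8 | 11.0 | 12.6 |
| Log-rank, patients, to 12 months (%) | 5.3 | 5.3 | 5.5 |
| Log-rank, patients, to 60 months (%) | 5.3 | 5.4 | 5.0 |

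The log-rank rows are simulated rejection rates at a nominal 5% for a patient-level factor with no effect (20,000 runs per ρ, exponential times, Gaussian copula, administrative censoring only). Wilson coverage should be read against 96.0%, its value for 112 independent units at p = 0.9.

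Varying b from 0.4 to 1.0 and ρ from 0.3 to 0.8 gives design effects of 1.17 to 1.80, and per-patient patency of 83.7% to 89.3% against 90% per side.

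**Step 3: direction.** The inflation applies to factors shared by both sides. For a factor that differs between a patient's two sides, as some lesion criteria may, the naive side-level log-rank test is conservative: at ρ = 0.5 it rejects about 1.5% of the time to 12 months and 0.5% to 60 months.

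**Step 4: occlusion rate.** Secondary Endpoint 2 names the event but no denominator. It can be read as grafts occluded or as patients with an occluded graft. The documents give no number of grafts per patient, so no effect has been computed for it.

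**The case for a change.** The strongest case for a change is that one result per patient is an inference. Neither the primary endpoint nor the SAP states it, and no sentence says that failure on one side is failure for the patient. On the illustration, the choice moves the headline rate between 87.3% and 90.0%, and a choice made after seeing the data could favour the better figure. Secondary Endpoint 2 stays open under any reading of target lesion. A few sentences would close all of this.

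Part of that stands: the unit is unwritten, and the occlusion rate has no denominator. But the harm needs three things together: the less-supported reading, no adjustment, and material correlation. The wording that defines the lesion already leads an analyst to the patient, and the either-side rule follows from it. An analyst reporting a graft-level rate would have to state its denominator anyway, and would use patient-clustered intervals.

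Rewriting the definition also carries a risk. A rule that patency is lost at the first stenosis or TLR would replace the visit-by-visit judgement in Secondary Endpoint 1, which is a change of endpoint and not of unit.

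One caution belongs with the patient-level reading itself. Bilateral patients have two chances to fail: 85.5% patent against 90% for unilateral patients at ρ = 0.5, with no per-side difference. A log-rank comparison of the two groups then rejects about 6.5% of the time to 12 months and 13% to 60 months. Such a contrast under the lesion criteria should not be read as a difference in performance per side.

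**Conclusion.** No change to the plan is needed. The documents leave out a sentence on the unit of analysis, but the definition of the target lesion and the wording of Secondary Endpoint 1 together give one patency result per patient. On that reading the intervals, life-tables and log-rank tests for patency are sound. The study is descriptive, with no performance goal and no formal test of the primary endpoint, so no pass/fail decision turns on the choice.

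The cost of the other reading (an interval half-width of 5.6 points where 6.5 is right, and 9.4% to 11.0% rejection at a nominal 5%, both at ρ = 0.5) arises only if sides are counted without adjustment, and rests on assumed values for bilateral share, patency and correlation. The remaining open item, the denominator of the occlusion rate, is a secondary descriptive detail of unquantified effect that can be stated when results are reported. This is a gap that analysts fill sensibly.

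### A below-knee amputation after the periprocedural period is counted as an event in no endpoint, although the objective is safety up to 60 months

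*Combined protocol and SAP*

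**What the plan says.** The Objective row of the synopsis sets out to evaluate the "long-term (up to 60 months) safety and efficacy of the Lifestream Peripheral Stent Graft System". Three places then decide which limb loss is counted.

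- **Safety endpoint (Primary Endpoint row).** "The primary safety endpoint of the study is the freedom of periprocedural Serious Adverse Events (SAEs"), with a seriousness definition that includes lasting disability and events needing surgery. The length of the periprocedural period is not given.
- **Secondary endpoint 4.** An amputation rate at every visit from 1 to 60 months, "defined as any amputation above the knee".
- **Statistical Analysis Plan.** Kaplan-Meier life-tables for all time-dependent events, from the procedure to the 60-month visit. The events are not listed, and no further safety endpoint is added.

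Angiographic inclusion criterion 1 lists five eligible lesion types. Three are explicitly bilateral: "Bilateral Common Iliac Artery occlusions", "Bilateral External Iliac Artery stenoses" of a stated length, and "Bilateral occlusions of External Iliac Artery". Endpoint 4 does not say whether amputations are counted per patient or per limb.

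**The concern.** The seriousness definition would catch an amputation at any level, but only in the periprocedural period. The amputation endpoint runs the full five years, but only for one level. A below-knee amputation at, say, two years falls between the two.

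The synopsis describes no comparator group, so the event rates themselves are the study's result. If the amputation rate at 60 months is quoted without its definition, a figure of 0% can be taken to mean that no leg was lost. The plan, followed exactly, would allow that figure to stand beside one or more below-knee amputations.

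**Working it through.** **Step 1: every endpoint against the same event.** Take a below-knee amputation that occurs after the periprocedural period and ask whether each endpoint counts it as an event.

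| Endpoint | Counted as an event? |
|---|---|
| Primary efficacy: patency at 12 months | No; depends on stenosis and TLR |
| Primary safety: periprocedural SAEs | No; outside the time window |
| Secondary 1: patency at other visits | No; depends on stenosis and TLR |
| Secondary 2: stent graft occlusion | No; the graft may or may not be occluded |
| Secondary 3: ABI | No; the value may be unobtainable on that limb |
| Secondary 4: amputation | No; below the level in the definition |
| Secondary 5: technical success | No; settled at the procedure |
| Secondary 6: clinical success | No; the patient may fail to show improvement |

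None of the eight counts it. Secondary endpoints 3 and 6 could be affected indirectly, but no rule says how ABI or Rutherford class is scored after an amputation.

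**Step 2: does the Statistical Analysis Plan close the gap?** It states how time-dependent events are to be analysed, not which events these are. Where amputation is analysed, the definition in force is that of endpoint 4.

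**Step 3: size.** There is no figure in the plan to reproduce. The documents give neither an amputation rate nor a derivation of the 70 subjects.

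Inputs: n = 70 (Enrollment row). Assumptions: all 70 are followed to 60 months, no above-knee amputation occurs, and there are k late below-knee cases. With complete follow-up, one minus the Kaplan-Meier estimate equals k/n. The intervals are exact (Clopper-Pearson).

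- Upper limit for 0/70: 1 − 0.025^(1/70) = 5.13%.
- Lower limit for 1/70: 1 − 0.975^(1/70) = 0.04%.
- Upper limit for 1/70: the p that solves (1 − p)^70 + 70p(1 − p)^69 = 0.025, which is 7.70%.

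| Late below-knee cases | Plan as written | Both levels counted |
|---|---|---|
| 1 | 0/70 = 0% (0 to 5.1%) | 1/70 = 1.4% (0.04 to 7.7%) |
| 2 | 0/70 = 0% (0 to 5.1%) | 2/70 = 2.9% (0.35 to 9.9%) |

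Each uncounted case moves the rate by 1/70 = 1.43 percentage points. With incomplete follow-up, a first event among r patients still at risk contributes 1/r to the Kaplan-Meier estimate. That is at least 1/70, so the illustration does not overstate the effect of one case.

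**The case against.** **The definition is stated openly.** Endpoint 4 gives the level in the same sentence as the rate, and the protocol never uses the term major amputation. This stands: it is a disclosed choice and not a hidden error. It does not answer the mismatch with the 60-month safety objective.

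**Amputation should be rare in these patients.** Entry is limited to Rutherford 2 to 4 with patent common and deep femoral arteries, and exclusion criteria 6 and 14 remove poor outflow and untreatable distal lesions. This is fair, and it means that few cases may be affected. But with 70 patients a single case changes the reported figure.

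**Later serious events may be recorded elsewhere.** The document is a synopsis, so this is possible. Recording an event does not make it part of an endpoint.

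Four stronger readings are tempting, and the documents do not support them.

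- *Long-term safety is not followed at all.* Above-knee amputation, occlusion and patency all run to 60 months. The gap shown here is one level of amputation.
- *The unit of counting is a flaw that could halve the rate.* Enrollment is in subjects and secondary endpoint 1 counts patients, so per patient is the natural default. A halving would need both limbs treated in every patient, and one eligible lesion type is explicitly unilateral. What remains is a wording gap.
- *Clinical success and ABI are wrongly defined because they include results after TLR.* The definitions ("Clinical success at follow-up is defined as an improvement of Rutherford classification" and ABI at each "month follow-up compared with the baseline ABI") set no TLR condition, unlike patency. Inclusion after TLR is therefore inferred from silence. Symptom status and ABI regardless of reintervention are valid measures, and any figure for the effect would be a product of two assumed rates.
- *No TLR rate will be reported.* TLR is a defined event that can be dated, and the commitment to life-tables for all time-dependent events can be read to cover it. The fair remark is only that it is not named.

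**Conclusion.** The point holds for amputation level. As written, a below-knee amputation after the periprocedural period is an event in none of the eight endpoints, while the objective claims safety to 60 months. The conclusion rests on the endpoint definitions alone and needs no assumed rate.

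The size does rest on assumptions: complete follow-up of 70 patients and a number of cases that the documents do not predict. Under these, one case is the difference between 0% (upper limit 5.1%) and 1.4% (upper limit 7.7%). The date from which the gap opens cannot be given, because the periprocedural period is undefined; that is a separate omission.

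This is an inexpensive improvement to a secondary endpoint and does not threaten the study's main result. No error is claimed in the definitions of clinical success or ABI.

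**What to change.** 1. Define the amputation endpoint to include below-knee as well as above-knee amputation, that is, any amputation above the ankle.
2. Report the two levels separately at each visit, and as a Kaplan-Meier time-to-event outcome to 60 months.
3. State that the count is per patient, and record the limb concerned, since three of the five eligible lesion types are bilateral.

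**Cost.** Amputation level and limb must be recorded; Table 1 lists neither explicitly, but a physical examination is already scheduled at every follow-up visit, so no visit or test is added. The reported rate may become slightly less favourable. Showing above-knee amputation on its own line keeps the present figure available.

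**Minor and optional.** Name TLR among the time-dependent events in the Statistical Analysis Plan, and label clinical success and ABI as regardless of reintervention. Both are changes of wording only.

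### Technical success has no stated denominator, and some procedural failures are also grounds for ineligibility, so the rate may be biased upward by an unknown amount

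*Combined protocol and SAP*

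**What the plan says.** The protocol synopsis lists, as secondary endpoint 5, "Technical success, defined as the ability to achieve final residual angiographic stenosis no greater than 30" per cent. Neither that entry nor the SAP paragraph names a denominator, an analysis set or a unit (patient or lesion).

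Four eligibility criteria bear on the same events:

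- Angiographic inclusion criterion 2 asks for a stenosis or restenosis above 50%, or an "occlusion which can be passed with standard guidewire manipulation".
- Exclusion criterion 1: "PTA is technically not possible (not feasible to access the lesion or a defect with the guidewire or balloon catheter").
- Exclusion criterion 5: "Heavily calcified lesions resistant to PTA".
- Exclusion criterion 19: "Perforation at the angioplasty site evidenced by extravasation of contrast medium".

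Table 1, in the row for the procedure, gives the order "Angiography, pre-procedure Study inclusion Intervention". On that order a patient is included before the treatment is attempted.

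The SAP is descriptive. It promises a 95% confidence interval for every variable and sets no target or expected rate for technical success.

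**The concern.** A lesion that is not crossed cannot end with a residual stenosis of 30% or less, and one that does not yield to the balloon is at high risk of missing that mark. These events are what a technical-success rate is meant to record, yet under the criteria above they also make the patient ineligible. The plan does not say which rule takes precedence.

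The title announces complex TASC C and D lesions. Three of the five qualifying lesion types are occlusions, so crossing is a real question here. A reader of the report would naturally take technical success as the chance of success when treatment of such a lesion is attempted. If patients in whom the attempt failed drop out as ineligible, the reported figure is instead the chance of success given that the lesion proved crossable and dilatable. Attempts that were not logged may be impossible to recover later.

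**Working it through.** **Step 1: set the passages side by side.** The plan states no technical success rate, so there is no figure to reproduce. The first check is how a failed attempt would be classified.

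- *Table 1 followed literally.* Eligibility is settled after angiography and before the intervention. A crossing or dilatation failure then occurs in an included patient. If all included patients are counted, it is a technical failure and there is no bias.
- *Criteria followed literally.* A perforation at the angioplasty site can be seen only once angioplasty has begun. Whether the guidewire passes, or the lesion resists PTA, may be suspected from imaging but may become clear only during the attempt. Such a patient then fails a criterion after the point at which Table 1 places inclusion. Nothing says whether the patient is a screen failure, is withdrawn after inclusion, or stays in as a technical failure.

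Both readings are open, and they give different denominators.

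**Step 2: how large could the effect be?** Let *f* be the share of all attempts that fail technically, and *s* the share of those failures removed as ineligible. Neither is in the documents; the values below are assumptions. It is also assumed that only failures are removed.

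- Success over all attempts: 1 − *f*
- Share of attempts remaining after exclusions: 1 − *fs*
- Failures among those remaining: *f*(1 − *s*)
- Reported success: 1 − *f*(1 − *s*)/(1 − *fs*)

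Worked example, *f* = 10% and *s* = 0.5: 1 − 0.05/0.95 = 94.7%, against 90% over all attempts, an excess of 4.7 points. In counts, 70 enrolled patients would come from 70/0.95 = 73.7 attempts, so about 3.7 failed attempts would be missing from the denominator.

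| *f* | Success, all attempts | Reported, *s* = 0 | *s* = 0.5 | *s* = 0.9 | *s* = 1 |
|---|---|---|---|---|---|
| 5% | 95% | 95.0% | 97.4% | 99.5% | 100% |
| 10% | 90% | 90.0% | 94.7% | 98.9% | 100% |
| 20% | 80% | 80.0% | 88.9% | 97.6% | 100% |

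The excess over this grid runs from 0 to 20 points. Its direction is fixed by the criteria; its size depends on *s*.

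**Step 3: compare with the planned interval.** With 70 patients, the exact 95% interval is 86.0% to 98.4% for 66/70 (94.3%), and 94.9% to 100% for 70/70. In the worked example the interval around the reported rate still contains 90%, so the bias is no larger than the sampling error. The interval does not allow for the bias, however, and at higher reported rates it can exclude the rate over all attempts.

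**The case against.** Four arguments carry weight.

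1. *Table 1 puts inclusion first.* If that order is kept and all 70 patients are counted, failures found later count against the endpoint. This stands as a possible reading, and it is why the bias may be zero. It does not remove the need to say so, because exclusion 19 in particular cannot be applied before the intervention.
2. *The population is a stated choice.* The objective covers the device "when used according to the indications of the IFU". That justifies who receives the stent graft and who enters the patency analysis. It does not justify leaving failed attempts unreported.
3. *The endpoint is secondary and descriptive.* It has no hypothesis or target, and the 12-month patency and safety endpoints are unaffected. This stands and limits the weight of the point.
4. *Perforation is not the same as residual stenosis.* A perforated lesion might still meet the 30% mark. It counts as a failure here only if the procedure is abandoned or the mark is missed.

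A reader might go further and infer that technical success will be close to 100% by construction, because its main failures have been removed. The documents do not support that. No criterion requires a residual stenosis of 30% or less. Exclusion 5 covers only heavily calcified lesions. Recoil, under-expansion, delivery failure or residual stenosis in a long or bilateral lesion can still be failures. The documents also give no breakdown of failures, so which are the main ones is unknown. With *f* = 10%, a reported rate near 99% would need about 90% of failures to be removed; and if the true rate among enrolled patients were 95%, the chance of 69 or 70 successes in 70 would be only 13%.

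**Conclusion.** The point holds as a gap in definition with a known direction and an unknown size. The plan makes some procedural failures grounds for ineligibility, places inclusion before the intervention, and gives no denominator. If the criteria are applied as written and these patients are left out, endpoint 5 is conditional on a crossable, dilatable lesion and biased upward as a measure of success when treatment is attempted.

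The bias is zero if every attempt is counted, and 4.7 points under the assumed 10% failure with half of the failures excluded. A reader might want one firm figure, for example by setting 69/70 = 98.6% against 69/77 = 89.6%. That comparison assumes a single counted failure and seven uncounted attempts, and the documents give neither. Nor should the point be read as hiding differences between sites: the plan foresees no comparison of sites.

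This is a minor point on a secondary descriptive endpoint, worth making because it is cheap to put right.

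**What to change.** Leave the eligibility criteria and the patency population as they are, and add to secondary endpoint 5 and the SAP:

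- **Denominator.** All consented patients who meet the criteria that can be judged before the attempt (qualifying lesion type, stenosis above 50% or occlusion, patent common and deep femoral artery), regardless of whether the guidewire passes, and in whom guidewire passage was attempted. The guidewire clause of angiographic inclusion 2 has to be set aside explicitly for this purpose. A denominator of angiographically eligible lesions would otherwise remove the crossing failures again.
- **Scoring.** Failure to cross, failure to dilate and abandonment of the procedure are technical failures, alongside a final residual stenosis above 30%.
- **Unit.** State whether it is the patient or the lesion. Three of the five qualifying lesion types are explicitly bilateral, so the choice affects the count.
- **Second rate.** Report the rate among treated patients beside the first, labelled 'in crossed and dilatable lesions', with the number of attempts and the exclusions by reason.
- **Timing.** Reconcile Table 1 with the criteria that can be known only during the procedure, by stating how a patient who meets one of them after inclusion is classified.

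The cost is this wording and a short log entry for each attempted but untreated patient, with no follow-up of those patients. The downside for the sponsor is a less favourable technical success rate if any failed attempts would otherwise have been left out.
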